		14.2.3.7.6 NYHA Functional Class – Subgroup of Sex - Full Analysis Set
		14.2.3.7.7 NYHA Functional Class – Subgroup of Age - Full Analysis Set
		14.2.3.7.8 NYHA Functional Class – Subgroup of Renal function at baseline - Full Analysis Set
		14.2.3.7.9 NYHA Functional Class – Subgroup of Ischaemic Aetiology of HF - Full Analysis Set

Type*	Section	Title
		14.2.3.7.10 NYHA Functional Class – Subgroup of NYHA at baseline - Full Analysis Set
		14.2.3.7.11 NYHA Functional Class – Subgroup of NT-pro BNP and BNP at baseline - Full Analysis Set
		14.2.3.7.12 NYHA Functional Class – Subgroup of Left ventricular ejection fraction (%) at baseline - Full Analysis Set
		14.2.3.7.13 NYHA Functional Class – Subgroup of Diagnosis of Heart Failure - Full Analysis Set
		14.2.3.7.14 NYHA Functional Class – Subgroup of Hospitalisation for Acute Heart Failure in the 12 months prior Index Hospitalisation - Full Analysis Set
		14.2.3.7.15 NYHA Functional Class – Subgroup of Creatinine at baseline - Full Analysis Set
		14.2.3.7.16 NYHA Functional Class – Subgroup of eGFR at baseline - Full Analysis Set
T	14.3 Safety	14.3.1.1 Overview of Adverse Events – Safety Analysis Set
		14.3.1.2 TEAEs by System Organ Class, Preferred Term and Treatment Group – Safety Analysis Set
		14.3.1.3 TEAEs Related to Study Product by System Organ Class, Preferred Term and Treatment Group – Safety Analysis Set
		14.3.1.4 TEAEs by System Organ Class, Preferred Term, Relationship to Study Product and Treatment Group – Safety Analysis Set
		14.3.1.5 Severe TEAEs by System Organ Class, Preferred Term and Treatment Group – Safety Analysis Set
		14.3.1.6 TEAEs by System Organ Class, Preferred Term, Severity and Treatment Group – Safety Analysis Set
		14.3.1.7 Serious TEAEs by System Organ Class, Preferred Term and Treatment Group – Safety Analysis Set
		14.3.1.8 Serious TEAEs occurring in >5% of subjects by System Organ Class, Preferred Term and Treatment Group – Safety Analysis Set
		14.3.1.9 Non-serious TEAEs by System Organ Class, Preferred Term and Treatment Group – Safety Analysis Set
		14.3.1.10 Serious TEAEs Related to Study Product by System Organ Class, Preferred Term and Treatment Group – Safety Analysis Set
		14.3.1.11 TEAEs Leading to Treatment Discontinuation by System Organ Class, Preferred Term and Treatment Group – Safety Analysis Set
		14.3.1.12 TEAEs Leading to Study Discontinuation by System Organ Class, Preferred Term and Treatment Group – Safety Analysis Set
		14.3.1.13 Serious TEAEs by System Organ Class, Preferred Term, Severity and Treatment Group – Safety Analysis Set
		14.3.1.14 Fatal TEAEs by System Organ Class, Preferred Term and Treatment Group – Safety Analysis Set
		14.3.1.15 Fatal TEAEs Related to Study Product by System Organ Class, Preferred Term and Treatment Group – Safety Analysis Set

Type*	Section	Title
		14.3.1.16 TEAEs of Clinical Interest by Event Type, Preferred Term and Treatment Group – Safety Analysis Set
		14.3.1.17 TEAEs of Special Interest Related to Study Product by Event Type, Preferred Term and Treatment Group – Safety Analysis Set
L	14.3.2 AE Listings	14.3.2.1 TEAEs Related to Study Product – Safety Analysis Set

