10.1.6 Suspected Unexpected Serious Adverse Reaction

Any ADR that is both serious and unexpected (per the RSI) that, based on the opinion of the Investigator or Sponsor, is felt to have a reasonable suspected causal relationship to a medicinal product.

Based on the specific study design and the advanced underlying disease state of the recruited subject population, events suggestive of the study outcomes i.e., a re-hospitalisation for an episode of acutely decompensated HF or a CV event leading to death which occurs after discharge for the Index hospitalisation would automatically

qualify to meet the criteria of seriousness in this study. These events would be reported as suspected unexpected serious adverse reactions in cases where there is reasonable suspected causal relationship to a medicinal product.

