4.6. Efficacy Evaluation

The analysis of the primary, secondary and other outcomes described below will be performed on the FAS. Sensitivity analyses will be performed on the PP analysis set.

Due to the Covid-19 pandemic, a sensitivity analyses will be performed for the primary and secondary endpoints on the FAS censoring subjects at index date. The index date is given for each country in the table below and corresponds with the first reported Covid-19 patient in the country. All events after the index date will be excluded and subject's follow-up time will be considered only up to the index date.

Table 4 Index Dates

Country	Index Date
Argentina	02-Mar-2020
Brazil	24-Feb-2020
Croatia	24-Feb-2020
Georgia	25-Feb-2020
Israel	20-Feb-2020
Italy	29-Jan-2020
Lebanon	20-Feb-2020
Netherlands	26-Feb-2020
Poland	03-Mar-2020
Romania	25-Feb-2020
Singapore	22-Jan-2020
Spain	30-Jan-2020
Sweden ¹	NA
United Kingdom ¹	NA
Ukraine	02-Mar-2020

¹ No active subject after the index date in this country.

All inpatient hospitalisations, all urgent heart failure visits, and all deaths will be reviewed by the Clinical Endpoint Committee (CEC) to determine whether they are CV-related or not. CV hospitalisations and urgent heart failure visits will be further adjudicated as due to worsening HF, myocardial infarction, unstable angina, and other CV event.

A death with a cause classified by the adjudication committee as “unknown” will be considered as a cardiovascular death. A death with a cause classified by the adjudication committee as “undetermined” will be considered as a non-cardiovascular death. For all other cases, the final adjudicated classification will be taken into consideration for the analyses described below.

Incomplete hospitalisation dates will be imputed in the following way:

Hospitalisation start date:

1. If the start date of a hospitalisation is partially missing and the month and year or the year are equal to those of the randomisation date and the hospitalisation end date is after or equal to the randomisation date or missing, then the hospitalisation start date will be imputed as the randomisation date.
2. If the hospitalisation end date is before the randomisation date, the hospitalisation start date will be imputed as the hospitalisation end date if the month and/or year is the same.
3. If the start date is completely missing, then the start date will be imputed as the hospitalisation end date.

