4.8.2. Adverse Events

Adverse events are to be recorded throughout the study, beginning at the moment of informed consent. AEs will be coded using MedDRA and displayed in tables and listings by SOC and PT.

Analyses of adverse events will be performed for those events that are considered treatment-emergent, where a treatment-emergent AE (TEAE) is defined as one that started, or worsened in severity or seriousness following the first dose of IMP. An AE with onset prior to the start of the administration of the first dose of study drug, or where the stop date is before the start of the administration of the first dose of study drug, or where the study drug injection was not started, will be considered as pre-study. In case the onset date is on the same day as the first dose of study drug and either the time of first dose or time of AE onset is missing, then AE is considered treatment-emergent.

AE intensity will be qualified as mild, moderate, or severe. The relationship to the study drug will be qualified as related (including categories certain, probable/likely, possible) or unrelated.

If the AE start date is missing or partial, the AE will be assigned to the appropriate period using available start date information and the stop date, if present.

Incomplete AE-related dates will be imputed in the following way:

AE start date:

- If the start date of an AE is missing completely, or is partially missing and the month and year or the year are equal to those of the first study drug start date and the AE end date is after or equal to the first study drug start date or missing, then the AE start date will be imputed as the first study drug start date. In case the end date of AE is the same as the IMP start date, non-missing times will also be checked.
- If the AE end date is before the first study drug start date, the AE start date will be imputed as the AE end date if month and/or year is the same.
- Otherwise the month and/or day will be replaced by January and/or 1.

AE end date:

- Incomplete stop dates will be imputed as the last day of the month (if only the day is missing), or the date of death, whichever is earlier.
- In all other cases the incomplete stop date will not be imputed.

Adverse events will be summarised by subject incidence rates, adjusted incidence rates, and number of events. An overview of TEAEs will present the numbers and percentages of subjects experiencing at least one event for the following categories:

- All AEs.
- TEAEs.

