- TEAEs by relationship to study drug.
- TEAEs by severity.
- Serious TEAEs.
- Related Serious TEAEs.
- Severe Serious TEAEs.
- TEAEs leading to treatment discontinuation.
- TEAEs leading to study discontinuation.
- All Fatal AEs.
- Fatal TEAEs.
- Related Fatal TEAEs.
- TEAEs leading to hospitalisation.
- TEAEs of clinical interest “CV Death” or “HF Hospitalisation”.
- TEAEs of special interest related to study drug.

Additionally, AEs in the categories listed below will also be summarised by incidence rates and adjusted incidence rates by SOC and PT, as well as number of events (Note: in the descriptive analysis for the incidence rate, each subject will contribute only once to the count for a given SOC or Preferred Term, regardless of the number of episodes experienced):

- TEAEs.
- TEAEs related to study drug.
- TEAEs by relationship (without adjusted incidence rates).
- Severe TEAEs.
- TEAEs by severity (without adjusted incidence rates).
- Serious TEAEs.
- Serious TEAEs occurring in > 5 % of the subjects.
- Non-serious TEAEs.
- Serious TEAEs related to study drug.
- TEAEs leading to treatment discontinuation, “drug withdrawn” in the eCRF.
- TEAEs leading to study discontinuation.
- Serious TEAEs by severity,
- Fatal TEAEs,
- Fatal TEAEs related to study drug,
- TEAEs of clinical interest (by PT only),
- TEAEs of special interest (by PT only) related to study drug.

Adjusted incidence rate will be calculated by dividing the number of subjects with a particular TEAE by the subject-years of time on study (see section 4.2.14) of all subjects in each treatment group.

In the tabulations by severity or relationship, each subject will contribute only once to each of the incidence rates by using the worst severity/strongest relationship reported within the period of interest; all events experienced will be counted in the event rates.

If the relationship is missing, the AE will be considered related to study drug. If the severity is missing, the AE will be considered to be severe.

Cardiovascular AE terms of clinical interest as reported by Investigators will be listed in this order in the table:

1. CV death
2. HF hospitalisation

The CV AEs of clinical interest as reported by Investigators will be identified as follows:

1. For HF hospitalisations: PT = “Cardiac failure”, “Cardiac failure acute”, “Cardiac failure congestive”. or “Cardiac failure chronic” and led to or prolonged hospitalisation = Yes

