4.8.4. Event Adjudication

Details on adjudications performed by the CEC will be tabulated for the SAF analysis set. The number of events adjudicated and the adjudication decisions will be summarised by treatment group, along with the number of hospitalisations adjudicated, the number of urgent HF visits (including emergency room and unscheduled outpatient visits), and the number of deaths adjudicated with cause of death.

Adjudication information will also be listed.

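### No pooled summary of serious TEAEs leaves out the efficacy endpoint events, so the pooled serious-event rows mix efficacy with safety

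*SAP*

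**What the plan says.** Protocol 10.1.6 states that a re-hospitalisation for decompensated HF, or a CV event leading to death, after the index discharge will automatically "qualify to meet the criteria of seriousness in this study". SAP 4.8.2 sets the measures: "Adverse events will be summarised by subject incidence rates, adjusted incidence rates, and number of events". Its overview (Table 14.3.1.1) counts subjects with at least one event in categories that include serious TEAEs and TEAEs leading to hospitalisation. The detailed table is "14.3.1.7 Serious TEAEs by System Organ Class, Preferred Term and Treatment Group – Safety Analysis Set", where "each subject will contribute only once to the count for a given SOC or Preferred Term, regardless of the number of episodes experienced".

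The endpoint-type events get an overview row and a table of their own, "14.3.1.16 TEAEs of Clinical Interest by Event Type, Preferred Term and Treatment Group – Safety Analysis Set". SAP 4.8.2 defines them by investigator-reported terms: four cardiac-failure preferred terms with hospitalisation for HF, and fatal events in the cardiac SOC plus sudden cardiac death for CV death. SAP 4.8.4 adds an adjudication table: "The number of events adjudicated and the adjudication decisions will be summarised by treatment group, along with the number of hospitalisations adjudicated". Neither SAP 4.8.2 nor the list of safety tables in SAP 7.1 takes endpoint events out of any serious-event summary.

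**The concern.** The sample size section (Protocol 12.2, SAP 4.1) expects about 35% of subjects to have an HF hospitalisation or CV death, and expects FCM to reduce HF hospitalisations by 30%. A pooled count of subjects with any serious TEAE is then driven in large part by the efficacy endpoint. If FCM works, the count falls on FCM for that reason alone, and can offset a rise in other serious events. If FCM does not work, the shared endpoint events dilute the contrast.

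Tolerability and safety are a stated secondary objective. An excess thinly spread over many preferred terms is best seen in a pooled total, and the planned pooled totals are the ones that carry the endpoint events.

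**Working it through.** **Inputs from Protocol 12.2 and SAP 4.1.** 12% of placebo subjects have a CV death, half of them without a prior HF hospitalisation (6%). 35% have any endpoint event, so 35 − 6 = 29% have at least one HF hospitalisation, averaging 2 each. FCM cuts HF hospitalisations by 30% and leaves CV death similar.

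**Inputs assumed.** The documents give no incidence of other serious events; 10% to 40% on placebo is used. Endpoint and other serious events are taken as independent. The 30% reduction is taken to act on the number of subjects hospitalised.

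**1. The plan's own figures.** Placebo: 12 + 2 × 29 = 70 events per 100 patient-years. FCM: 12 + 0.7 × 58 = 52.6. Ratio 52.6/70 = 0.751, which reproduces the planned 0.75. The plan states no figure for serious TEAEs.

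**2. Subjects with an endpoint event.** Placebo e0 = 35%. FCM e1 = 6% + 0.7 × 29% = 26.3%.

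**3. When the pooled row looks level.** With h the incidence of other serious events, the pooled row is 1 − (1 − e)(1 − h). The arms are equal when h1 = 1 − 0.65(1 − h0)/0.737. So other serious incidence can rise on FCM from 10% to 20.6%, 20% to 29.4%, 30% to 38.3% or 40% to 47.1% (ratios 2.06, 1.47, 1.28, 1.18) with no difference in the pooled row.

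**4. A 25% relative excess of other serious events on FCM.**

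| Other serious, placebo vs FCM | Pooled row, placebo | Pooled row, FCM |
|---|---|---|
| 20% vs 25% | 1 − 0.65 × 0.80 = 48.0% | 1 − 0.737 × 0.75 = 44.7% |
| 30% vs 37.5% | 1 − 0.65 × 0.70 = 54.5% | 1 − 0.737 × 0.625 = 53.9% |
| 40% vs 50% | 1 − 0.65 × 0.60 = 61.0% | 1 − 0.737 × 0.50 = 63.15% |

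The sign turns where 0.65(1 − h) = 0.737(1 − 1.25h), i.e. h = 0.087/0.27125 = 32%. With a weaker efficacy effect it turns sooner: at e1 = 28%, 0.65(1 − h) = 0.72(1 − 1.25h) gives h = 0.07/0.25 = 28%.

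**5. No efficacy.** With 35% in both arms, 20% against 25% gives 48.0% against 1 − 0.65 × 0.75 = 51.25%. A 5.0-point excess shows as 3.25 points.

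**6. Event counts.** Endpoint events fall by 70 − 52.6 = 17.4 per 100 patient-years. An equal excess of other serious events leaves the total level: a rate ratio of (20 + 17.4)/20 = 1.87 if the placebo rate of other serious events is 20 per 100 patient-years, and by the same formula 1.44 at 40, 1.29 at 60 and 1.17 at 100 (assumed range).

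**7. Subtraction does not recover the count.** Taking the clinical-interest row from the serious row leaves subjects with other serious events and no endpoint event, (1 − e)h; subjects with both are lost. That remainder also moves with efficacy. With 20% in both arms, so no harm at all, it would read 0.65 × 0.20 = 13.0% against 0.737 × 0.20 = 14.7%. Subtracting event counts is only approximate, because a fatal HF hospitalisation can meet both clinical-interest definitions.

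**The case against.** A reader might infer that the remaining serious events are not summarised at all. The documents do not support that. Table 14.3.1.7 breaks serious TEAEs down by SOC and preferred term and arm, and HF terms do not enter the infection, renal, hepatic or immune rows. An excess concentrated in one non-cardiac SOC would show there unmasked. This stands, and confines the problem to pooled totals: the overview rows, any line for subjects with any event, and the Cardiac Disorders SOC total.

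A reader might extend the argument to the fatal rows. The plan assumes similar CV death in the two arms, so on its own assumptions no CV-death benefit is there to offset other deaths. The CEC reviews all deaths (SAP 4.6), Table 14.4.1.1 gives adjudicated deaths with cause by arm, and all-cause and CV mortality to 52 weeks are both analysed. Non-CV deaths are therefore already visible. This part of the objection also stands.

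A reader might also expect the serious-event comparison to reverse as a rule. It does not: in step 4 the direction is correct once other serious events exceed about 32% on placebo, and that incidence is not in the documents. Safety is descriptive (Protocol 12.8), so no planned test changes.

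What the objection leaves untouched is the diffuse excess. Table 14.4.1.1 is described in numbers of events and decisions, and covers hospitalisations, urgent HF visits and deaths. Events serious on other grounds, such as medically important ones, need not appear in it.

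**Conclusion.** The point holds in a limited form. The SAP plans no pooled summary of serious TEAEs without the endpoint events, and the number of subjects with any other serious TEAE cannot be recovered from the planned tables. On the plan's efficacy assumptions, the pooled row would look level despite a rise in other serious events from 20% to 29.4%, or from 30% to 38.3%. Masking weakens as other serious events become more common. These sizes rest on independence, on an assumed placebo incidence of other serious events, and on the 30% reduction acting on subjects. No primary or secondary efficacy inference is affected; the value lies in a clearer safety comparison.

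**What to change.** Keep all existing tables. In SAP 4.8.2 and Table 14.3.1.1 add two rows: serious TEAEs excluding HF hospitalisation and CV death, and TEAEs leading to hospitalisation excluding HF hospitalisation. Add one SOC/PT table of serious TEAEs with the same exclusion on the Safety set, giving subjects, events and adjusted rates by arm.

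Apply the exclusion to AE records, not to subjects, so that a subject with both kinds of event still counts. Base it on CEC-confirmed events, but do not exclude deaths the CEC classed as unknown: SAP 4.6 counts these as CV deaths for efficacy, and removing them here would drop unexplained deaths from the safety summary. Repeat the output with the investigator-reported definition behind Table 14.3.1.16. No separate fatal row is needed. Specify this before unblinding.

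The cost is slightly more safety output and the linking of AE records to CEC decisions. Protocol 9.2.3.14 has reported AEs assessed and passed to the CEC, and SAP 2.5.4 lists adjudicated AEs among the safety endpoints, so a link is likely to exist, but neither document describes a record-level key. That should be confirmed first.

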		14.3.2.2 Serious TEAEs Related to Study Product – Safety Analysis Set
		14.3.2.3 Fatal Adverse Events – Safety Analysis Set
L	14.3.4 Labs Listing	14.3.4 Abnormal Laboratory Values – Safety Analysis Set
T	14.4 Other Safety	14.4.1.1 Summary of Event Adjudications Performed by CEC – Safety Analysis Set
		14.4.2.1 Summary of Special Situation Events – Safety Analysis Set
		14.4.3.1.1 Laboratory Values: Actual Values and Changes from Baseline by Analysis Visit for Serum ferritin (ng/mL) – Safety Analysis Set
		14.4.3.1.2 Laboratory Values: Actual Values and Changes from Baseline by Analysis Visit for Haemoglobin (g/L) – Safety Analysis Set
		14.4.3.1.3 Laboratory Values: Actual Values and Changes from Baseline by Analysis Visit for Transferrin saturation (%) – Safety Analysis Set
		14.4.3.1.4 Laboratory Values: Actual Values and Changes from Baseline by Analysis Visit for Phosphorus (mg/dL) – Safety Analysis Set
		14.4.3.2.1 Shift from Baseline and Post-Baseline Analysis visits for Normal versus Abnormal Laboratory Values for Serum ferritin (ng/mL) – Safety Analysis Set
		14.4.3.2.2 Shift from Baseline and Post-Baseline Analysis visits for Normal versus Abnormal Laboratory Values for Haemoglobin (g/L)– Safety Analysis Set
		14.4.3.2.3 Shift from Baseline and Post-Baseline Analysis visits for Normal versus Abnormal Laboratory Values for Transferrin saturation (%) – Safety Analysis Set
		14.4.3.2.4 Shift from Baseline and Post-Baseline Analysis visits for Normal versus Abnormal Laboratory Values for Phosphorus (mg/dL) – Safety Analysis Set
		14.4.3.3 Shift from Baseline and Post-Baseline Analysis visits and Lowest Post-Baseline Value for Phosphorus (mg/dL) – Safety Analysis Set
		14.4.4.1.1 Vital Signs: Actual Values and Changes from Baseline by Analysis Visit for Height (cm)– Safety Analysis Set
		14.4.4.1.2 Vital Signs: Actual Values and Changes from Baseline by Analysis Visit for Weight (kg)– Safety Analysis Set

Type*	Section	Title
		14.4.4.1.3 Vital Signs: Actual Values and Changes from Baseline by Analysis Visit for Systolic blood pressure (mmHg) – Safety Analysis Set
		14.4.4.1.4 Vital Signs: Actual Values and Changes from Baseline by Analysis Visit for Diastolic blood pressure (mmHg)– Safety Analysis Set
		14.4.4.1.5 Vital Signs: Actual Values and Changes from Baseline by Analysis Visit for Heart rate (beats/min) – Safety Analysis Set
		14.4.4.1.6 Vital Signs: Actual Values and Changes from Baseline by Analysis Visit for Pulse (beats/min) – Safety Analysis Set
		14.4.4.1.7 Vital Signs: Actual Values and Changes from Baseline by Analysis Visit for Temperature (°C) – Safety Analysis Set
		14.4.5.1 Electrocardiogram: Shifts from Baseline and Week 52 Visit for Overall Interpretation – Safety Analysis Set
		14.4.5.2 Electrocardiogram: Shifts from Baseline and Last Available Value for Overall Interpretation – Safety Analysis Set
		14.4.5.3 Electrocardiogram: QT Analysis – Safety Analysis Set
T	14.5 Quality of Life	14.5.1.1.1 KCCQ-12: Actual Values and Changes from Baseline – Full Analysis Set
		14.5.1.1.2 KCCQ-12: Actual Values and Changes from Baseline – Per Protocol Set
		14.5.1.2.1 KCCQ-12 Repeated-Measures Model for Analysis of Treatment Difference (Overall Summary Score) – Full Analysis Set
		14.5.1.2.2 KCCQ-12 Repeated-Measures Model for Analysis of Treatment Difference (Overall Summary Score) – Per Protocol Set
		14.5.1.3.1 KCCQ-12 Repeated-Measures Model for Analysis of Treatment Difference (Clinical Summary Score) – Full Analysis Set
		14.5.1.3.2 KCCQ-12 Repeated-Measures Model for Analysis of Treatment Difference (Clinical Summary Score) – Per Protocol Set
